10.1.3 Secondary Endpoint: Analysis of Seizure Outcomes

Seizure frequency will be characterized by calculating the rate of seizure occurrence within specific follow-up time periods (count of reported events/reported time frame). Follow-up time periods of interest include all follow-up and between-visit follow-up periods (e.g., procedure to Month 3) to characterize the longitudinal course of seizure frequency. For each time period, descriptive statistics of subject-specific rates characterize the distribution of observed seizure rates. The change from baseline in seizure rates may also be calculated by calculating the difference in rates between a follow-up period and the baseline rate of seizures occurring prior to treatment (count of reported events/reported time frame). Since subjects may have different baseline seizure rates, the relative reduction (follow-up rate/baseline rate - 1) will also be calculated to scale the degree of improvement relative to the baseline rate. These analyses may be repeated for subsets of seizures with specific classifications to characterize the frequency of different seizure types.

The main analysis of seizure frequency will include subjects with at least 70 completed diary days in each 3-month period from procedure through 12 months and at least 140 diary days in each 6-month period from 12 months through study completion. To account for incomplete diary completion, sensitivity analyses may be performed by including subjects with less than the required level of diary completion and by using the number of days with completed diary entries to determine the denominator in the event rate calculation.

Seizure frequency may be further characterized by calculating the proportion of responders. A responder is a subject whose seizure frequency in a specified 3-month interval is reduced by $\geq 50\%$ as compared to baseline.

Seizure free days may be further characterized by calculating the number of seizure-free days that subjects experience during a specified 3-month interval. In order to make the 3-month

follow-up intervals comparable, the number of days actually recorded will be prorated to an 84-day intervals.

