The primary analysis of seizure frequency will include subjects with at least 70 completed diary days in each 3 month period from procedure through 12 months and at least 140 diary days in each 6 month period from 12 months through study completion. To account for incomplete diary completion, sensitivity analyses may be performed by including subjects with less than the required level of diary completion and by using the number of days with completed diary entries to determine the denominator in the event rate calculation.

Seizure frequency may be further characterized by calculating the *proportion of responders*. A responder is a subject whose seizure frequency in a specified 3-month interval is reduced by $\geq 50\%$ as compared to the 3-month Baseline Phase.

Seizure free days may be further characterized by calculating the percent change in seizure-free days that subjects experience during a specified 3-month interval compared to Baseline. In order to make the 3 month follow-up intervals and the Baseline Phase comparable, the number of days actually recorded will be prorated to an 84-day interval for both intervals. Seizure-free days may also be expressed as a proportion of the number of follow-up days with available diary data.

Freedom from seizures with altered awareness will be reported using Kaplan-Meier curve analysis. Seizures with altered awareness include those categorized as either “impairment of consciousness or responsiveness” or “evolving to a bilateral, convulsive seizure”. The time to event analysis will exclude seizures that occur within the first 4 weeks post-procedure. The event time will be calculated using the earliest post-treatment date of a seizure with altered awareness, as reported in subject diaries. The censoring date will be the last completed diary date for subjects without seizures with altered awareness. The Kaplan-Meier analysis may be repeated for freedom from all seizures, seizures with other classifications, and inclusion of seizures within the first 4 weeks post-procedure. The log-log transformation will be used to calculate 95% confidence intervals. The time point of primary interest is 24 months.

Longest seizure-free interval will be characterized with descriptive statistics for each 3-month period and cumulatively over consecutive 3-month periods. The seizure-free interval will be

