12.3 Duration variables

Months for this study are defined as 28-day intervals and are referred to as "study months" to distinguish the interval from calendar months. Duration in study months is calculated as the number of days divided by 28. Duration in study years is calculated as the number of days divided by 12 study months.

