12.4 Rate variables

Rates will be calculated as the ratio of the number of events divided by the number of days over which data collection occurred. Rates may be reported as events per day, per study month, or per study year. For diary data, days on which episode data is not available will not be included in the denominator.

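### The denominator of the main seizure rate is not settled: Protocol 10.1.3 and SAP 11.1.3 imply it is not completed diary days, while SAP 12.4 requires that days without diary data be left out

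*Protocol*

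**What the plan says.** Protocol 10.1.3 defines the seizure rate as "count of reported events/reported time frame", and SAP 11.1.3 uses the same formula. Neither says whether the time frame means elapsed days or days with a diary entry.

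Entry to the main analysis depends on diary completeness. For the first year the Protocol asks for "at least 70 completed diary days in each 3-month period from procedure through 12 months". For the second year its requirement is "at least 140 diary days in each 6-month period from 12 months through study completion". SAP 11.1.3 sets the same thresholds. It then continues: "To account for incomplete diary completion, sensitivity analyses may be performed by including subjects with less than the required level of diary completion". A second option follows within that sentence, namely to compute the rate "by using the number of days with completed diary entries to determine the denominator in the event rate calculation". The Protocol sentence is to the same effect.

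SAP 12.4, in the general section on rates, is unconditional: "For diary data, days on which episode data is not available will not be included in the denominator". Protocol Rev B contains no equivalent.

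On interval length, SAP 12.3 says "Months for this study are defined as 28-day intervals". The Protocol does not define a month. It gives an 84-day length only for seizure-free days, where "the number of days actually recorded will be prorated to an 84-day intervals".

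**The concern.** A denominator offered as an optional way to account for incomplete diaries suggests that the main analysis uses a different one. The obvious alternative is the elapsed interval. In that case, days marked NAV (Protocol Appendix B) would add time to the denominator but no seizures to the numerator, as though they were seizure-free.

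SAP 12.4 says the reverse, and neither document states which text takes precedence. Two analysts could follow the plan and report different main rates from the same diaries. The difference would carry into the relative change from baseline, the responder proportion and the site-level Poisson regression in SAP section 19.

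The study is single-arm, so no control group would absorb an error in the follow-up rate. Under Protocol Rev B the baseline comes from retrospective history (Appendix B) and not from the study diary, so missing diary days would lower the follow-up rate alone. Protocol 10.2.4 intends the results to inform planning of a larger pivotal trial.

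**Working it through.** **The plan's own figures.** The documents give no figure for the effect of missing diary days. The one length that can be checked is the interval: 3 × 28 = 84 days, which agrees with the 84 days in Protocol 10.1.3. By the same rule 6 × 28 = 168 days.

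**Inputs**
- Diary floor: 70 days per 3 months and 140 per 6 months (Protocol 10.1.3, SAP 11.1.3).
- Interval length: 84 and 168 days under SAP 12.3. Calendar months of about 91 and 182 days are an assumption, made because the Protocol does not define a month.
- Responder: a reduction of at least 50% in a 3-month interval (both documents).
- Further assumptions: no seizures are counted on unrecorded days, the true rate is the same on recorded and unrecorded days, and the baseline rate is unaffected.

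**Step 1: understatement if elapsed days are the denominator.** Let f = completed days / elapsed days. The rate is understated by 1 − f.
- 28-day months, at the floor: f = 70/84 = 140/168 = 0.833, understatement 16.7%.
- Calendar months, at the floor: f = 70/91 = 140/182 = 0.769, understatement 23.1%. With 90 and 180 days it is 22.2%.
- 80 of 84 days completed: f = 0.952, understatement 4.8%.

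Dividing by completed days would raise the floor subject's rate by 84/70 = 1.20, or by 91/70 = 1.30 with calendar months.

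**Step 2: apparent reduction.** Apparent reduction = 1 − f × (1 − true reduction).

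| True reduction | Shown at 70/84 |
|---|---|
| 0% | 16.7% |
| 40% | 50.0% |
| 50% | 58.3% |
| 90% | 91.7% |

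The true reduction that just reaches the responder cut-off is 1 − 0.5/f. This is 40% at 70/84, 35% at 70/91 and 47.5% at 80/84. A subject with no seizures has a rate of zero under any denominator.

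**Step 3: the passages side by side.**
- If SAP 11.1.3 is read as making completed days a sensitivity option only, the main denominator must be something else, and SAP 12.4 is contradicted.
- If SAP 12.4 governs, the main analysis already uses completed days, and naming that denominator as a separate sensitivity option adds nothing for subjects above the threshold.

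Either way the text needs to be reconciled.

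**The case against.** The strongest reply is that the SAP already contains the right rule. SAP 12.4 is mandatory and is not confined to sensitivity analyses. The undefined time frame can naturally mean the time for which reports exist. Neighbouring measures point the same way: seizure-free days are prorated from recorded days, and SAP 11.1.3 counts the longest seizure-free interval in completed diary days. The disputed sentence can also be read as one combined sensitivity analysis, which adds subjects below the threshold and computes their rates on completed days. Read so, it does not contradict SAP 12.4.

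Much of this stands. A reader might infer that the plan keeps missing days in the main denominator and that rates will be understated by up to 17%. The documents do not support that. No passage states such a rule, SAP 12.4 says the opposite, and 17% is neither a group average nor a ceiling.

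The direction of net bias is also less certain than the arithmetic suggests. A retrospective baseline may itself be miscounted. The SAP, written against Protocol Rev A, assumes a 3-month baseline diary phase, in which missing days could partly offset those in follow-up.

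The reply does not remove the ambiguity. Even on the combined reading, neither endpoint section says what the main denominator is. The current Protocol has no counterpart to SAP 12.4 to fall back on.

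**Conclusion.** The conflict is real and should be fixed. The endpoint sections imply one main denominator, the SAP's general rule requires another, and Protocol Rev B is silent.

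The possible error is conditional. It arises only if elapsed days are used. It then reaches 16.7% (28-day months) or about 23% (calendar months) for a subject at the diary floor who still has seizures. It falls to 4.8% at 80 of 84 days and to zero for seizure-free subjects, and the distortion of the percent reduction shrinks as the true reduction grows. These figures assume equal seizure rates on recorded and unrecorded days. The net bias in change from baseline also depends on how accurate the baseline count is.

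Seizure frequency is a descriptive secondary endpoint in a feasibility study of about 30 treated subjects with no hypothesis tests, and the responder analysis is itself optional. The primary safety endpoint and the Kaplan-Meier analysis, which works from diary dates, do not use this denominator. The point therefore does not threaten the study's main conclusions.

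**What to change.** In Protocol 10.1.3 and SAP 11.1.3, define the main seizure rate as seizures divided by completed (non-NAV) diary days in the interval, citing SAP 12.4. State that responder status follows from that rate. Remove this denominator from the optional sensitivity list, and keep the inclusion of subjects below the 70-day and 140-day thresholds as the sensitivity analysis.

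The cost is about one sentence in each document and no new data. The downside is that reported reductions may be slightly smaller than with an elapsed-day denominator. The choice should be fixed before seizure outcomes are analysed.

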6.3.1 Study Inclusion Criteria

Subjects must meet all of the following inclusion criteria:

1. Diagnosis of unilateral medial temporal lobe epilepsy (MTLE) confirmed clinically and with either (1) ictal scalp recording and MRI evidence of mesial temporal sclerosis or (2) intracranial ictal onset consistent with hippocampal origin
2. Subject's seizures are distinct, stereotypical events that can be reliably counted.
3. Based on medical record, history of an average of at least 1 complex partial or secondarily generalized seizure compatible with MTLE per month for a minimum of the last 12 months prior to the Baseline visit (i.e., at least 12 qualifying seizures in the 12 months prior to the Baseline visit). *(Seizures occurring during inpatient assessment in an epilepsy monitoring unit should not be included in the average).*
4. Subject is on stable antiepileptic drugs (AEDs) for 30 days prior to the Baseline visit and compliant with medication use (as reported by the subject). Stable is defined as no new or discontinued AEDs and no changes to AED total daily dose. *(Exception: (1) temporary changes or discontinuation of AEDs for the purposes of diagnostic or medical procedures during the 30 days preceding the Baseline visit and (2) acute, intermittent use of benzodiazepines or other rescue medications.)*
5. Subject has met the criteria for a medial temporal lobe resection based on the Site's standardized pre-surgical evaluation.
6. Subject is deemed a LITT candidate by the center's epilepsy evaluation team.
7. Subject is 18 years or older at the time of consent.
8. Subject can be reasonably expected to maintain a seizure diary alone or with the assistance of a caregiver.
9. If female, must be postmenopausal, surgically sterile, or, if of childbearing potential, have a serum pregnancy test with a negative result at the Baseline visit and practicing effective contraception.³
10. Subject or legally authorized representative is able to provide appropriate consent to participate.
11. Subject is able to complete regular office and telephone appointments per the protocol requirements.
12. Subject speaks English or Spanish as a primary language. If Spanish, the Site must be able to provide a translated (IRB-approved) consent form and the Site's neuropsychologist must be willing and able to assess the subject in Spanish.

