7.6 Procedures and Subject Assessments

7.6.1 Baseline Visit

Prior to consenting patients for the study, Site personnel will evaluate potential candidates by reviewing the patient medical records against the study eligibility criteria. It is expected that the medical records will contain adequate information to determine if the patient meets these criteria. Potential patients will be asked to complete the informed consent process.

The following evaluations and assessments will be performed at this visit:

- Demographics
- Medical, surgical and epilepsy history
 - Epilepsy history will include collection of 12 months of retrospective seizure frequency data; data from the 3 months prior to the Baseline visit will be used for eligibility determination. See Appendix B for more details.
- Quality of Life in Epilepsy - 31 (QOLIE-31). It is preferred that the subject completes the questionnaire prior to any other baseline tests.
- Medication review, including collection of 12 months of retrospective epilepsy medication data (as available) to qualitatively assess medication stability prior to the NeuroBlate procedure. See Appendix A for more details.
- Physical exam
- Neurological exam
- Visual field testing (automated perimetry)
- Serum pregnancy test (if female and of childbearing potential)
- Neuropsychological testing (see Appendix C).
- Functional assessment (including employment status, education, living arrangements, driving status)
- Seizure classification assessment
- Seizure diary training

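### The optional responder analysis uses one unnamed 3-month interval, so a subject at the entry floor of 1 seizure per month would be a responder by chance about 20 to 26% of the time

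*Protocol*

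**What the plan says.** Protocol 10.1.3 introduces the analysis as optional: "Seizure frequency may be further characterized by calculating the proportion of responders". It then gives the rule: "A responder is a subject whose seizure frequency in a specified 3-month interval is reduced by" at least 50% compared with baseline. It does not say which 3-month interval is meant or how long the baseline is. SAP 11.1.3 repeats the rule but compares with a 3-month Baseline Phase.

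Protocol 6.3.1, criterion 3, requires a "history of an average of at least 1 complex partial or secondarily generalized seizure compatible with MTLE per month", spelled out as "at least 12 qualifying seizures in the 12 months prior to the Baseline visit". Protocol 7.6.1 collects 12 months of retrospective seizure data but states that "data from the 3 months prior to the Baseline visit will be used for eligibility determination". Appendix B likewise names 3 months for eligibility and collects 12 months of counts if available.

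On interval length, SAP 12.3 states "Months for this study are defined as 28-day intervals", and for seizure-free days the protocol says "the number of days actually recorded will be prorated to an 84-day intervals". The main seizure-frequency analysis requires "at least 70 completed diary days in each 3-month period from procedure through 12 months".

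The SAP cites protocol Rev A. Its visit table has a prospective diary baseline from Week -12 to Week 0, and its per-protocol rule still requires 3 or more seizures per month. In Rev B, diaries start the day after discharge (Appendix B).

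**The concern.** A 50% criterion is informative only if the window holds enough expected events for a halving to be unusual. At the entry floor the window holds about three. The study has a single arm, so nothing subtracts the chance component from a reported responder proportion. Protocol 10.2.4 says the results should help plan for the range of outcomes in a larger pivotal trial. A proportion with an unstated chance component is a weak basis for that.

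The plan already follows the relevant principle elsewhere. For neuropsychological change, both documents set a threshold that measurement error alone crosses less than 2.5% of the time in either direction, and SAP 11.1.2 reads observed proportions against 2.5%. The responder rule has no such calibration.

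**Working it through.** **The plan's own figure.** The documents give no chance-responder rate to reproduce. Their only design probability, in Protocol 10.2.4, checks: 1 - 0.95^30 = 0.785, stated as approximately 80%.

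**Inputs.** The floor is 12 per 12 months (criterion 3), which gives 12/4 = 3.0 per calendar quarter, or 12 x 84/365.25 = 2.76 per 84 days. A responder has a rate no more than half of baseline. Assumptions not in the documents: Poisson counts, an unchanged true rate, and independent baseline and follow-up periods.

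**Step 1: baseline rate known exactly.** Half of 3.0 is 1.5 and half of 2.76 is 1.38, so a responder has 0 or 1 seizure.
- Calendar quarter: P(X ≤ 1 | 3.0) = 4e^-3 = 19.9%.
- 84 days: P(X ≤ 1 | 2.76) = 3.76e^-2.76 = 23.8%.
- Twelve months, for comparison: P(X ≤ 6 | 12) = 4.6%.

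**Step 2: baseline counted, with entry at 12 or more.** With true monthly rate λ, 12-month baseline count b and follow-up window of w months, the chance rate is the sum over b ≥ 12 of Pois(b; 12λ) x P(X ≤ floor(0.5·b·w/12) | wλ), divided by P(B ≥ 12).

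| True rate per month | 3 months, baseline known | 3 months, entry ≥ 12 | 11 months, entry ≥ 12 | 12 months, entry ≥ 12 |
|---|---|---|---|---|
| 1 | 19.9% | 26.5% | 9.7% | 10.7% |
| 1.5 | 17.4% | 16.4% | 3.1% | 3.0% |
| 2 | 15.1% | 11.7% | 1.4% | 1.3% |
| 3 | 5.5% | 6.7% | 0.3% | 0.3% |

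The floor entry in the third column is 26.45% before rounding, hence a floor-level range of about 20 to 26%. The 11-month column approximates the end of week 4 to Month 12. If Month 12 is read as 12 x 28 = 336 days, the window is 336 - 28 = 308 days, or 10.1 calendar months, and the first three rows become 11.4%, 3.5% and 1.6%.

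**Step 3: sensitivity at the floor.**
- Variance twice the mean (negative binomial), entry ≥ 12: 40.2% over 3 months against 23.9% over 12 months.
- Only 70 diary days, baseline known: the mean is 12 x 70/365.25 = 2.30, and P(X ≤ 1) = 33.1%.
- A retrospective 3-month baseline with at least 3 seizures, against a 3-month follow-up: 37.2%.
- The SAP's carried-over floor of 3 per month (9 per quarter), baseline known: P(X ≤ 4 | 9) = 5.5%.

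**Step 4: the unnamed interval.** If any one of four independent quarters could be used, a floor-level subject with no change would qualify at least once with probability 1 - (1 - 0.199)^4 = 59%, or 66% with 84-day intervals. This shows why the interval should be fixed; it does not describe what the plan says will be done.

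**The case against.** The best case against acting is that little rests on this analysis. It is optional, secondary and descriptive, with no hypothesis test, success criterion or sample size attached. The plan already commits to outcomes on longer horizons: seizure rates over all follow-up with relative change from baseline, Kaplan-Meier seizure freedom with 24 months of primary interest, and Engel and ILAE classes at scheduled visits. The ILAE boundary between classes 4 and 5 is itself a 50% reduction in seizure days against the 12 months before surgery. All of this stands, and it limits the point to how one optional summary is defined.

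Three stronger readings are tempting, and the documents do not support them.
- **That a fifth to a quarter of the whole cohort would be responders by chance.** The figure belongs to the floor and falls quickly with rate. Selection on a high past count also matters mainly there: P(B ≥ 12) is 54% at a true rate of 1, but 94.5% at 1.5 and 99.8% at 2. The baseline distribution is not given. Criterion 3 counts only complex partial or secondarily generalized seizures, while the responder text says seizure frequency without that limit. A floor-level subject with other counted seizures would have a lower chance rate.
- **That the interval will be picked after seeing the data.** The text says the interval is specified; it omits which one.
- **That the responder proportion carries no information about treatment.** That does not follow when the cohort's chance rate is unknown.

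The longer window is not free of problems either. AEDs are to be held stable only through Month 12, with exceptions in Appendix A, so a Month 12 to 24 status mixes the procedure with medication changes. An additional LITT procedure (Protocol 7.7) could fall inside a year-long window. The floor-level chance rate remains about 10%, and is higher if seizures cluster.

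**Conclusion.** The point holds as a modest, inexpensive improvement to an optional analysis. At the entry floor, with no true change, a 3-month responder status arises by chance about 20 to 26% of the time. A window from week 4 to Month 12 against a 12-month baseline brings this to about 10%. At 1.5 and 2 per month the drop is from about 16% to 3% and from about 12% to 1.4%. The longer window gives the lower rate at every true rate checked.

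The levels rest on Poisson counts, independence and an unchanged true rate. Overdispersion, fewer diary days or a short baseline raise them; additional counted seizure types lower them.

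The SAP wording needs revision in any case. Its comparator belongs to the Rev A baseline diary, and substituting a retrospective 3-month baseline at the current floor would raise the chance rate to about 37%. Type I error, sample size and the committed seizure outcomes are untouched.

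**What to change.** If responders are reported:
1. Define the headline responder status over the end of week 4 to Month 12, against the 12-month retrospective baseline of criterion 3. The 4-week start matches the exclusion already used for the Kaplan-Meier, Engel and ILAE outcomes.
2. Count the same seizure types in both periods, and state how subjects with an additional LITT procedure are handled.
3. Replace the 3-month Baseline Phase wording in SAP 11.1.3, and reconcile the SAP's 3-per-month per-protocol criterion with criterion 3.
4. Report 3-month responder proportions for every interval, as time course only.
5. Treat any Month 12 to 24 status as supportive, because the AED restriction ends at Month 12.

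The cost is wording in the protocol and SAP. There would be no early headline responder figure, and the reported proportion may be slightly lower. Twelve-month baseline counts would be needed for every subject. Criterion 3 already requires them, but Protocol 7.6.1 and Appendix B name 3 months for eligibility and Appendix B collects 12 months only if available, so those passages must be reconciled first.
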